10.7 Adverse Event Follow-up

All unresolved SAEs ("ongoing" at discharge) will be followed by the study staff until resolution or deemed stable.

10.8 Adverse Events of Special Interest

10.8.1 Localized Signs of Infection or Inflammation at the Injection Site

Events that, in the opinion of the Investigator, may represent localized signs of infection or inflammation at the XT-150 injection site (e.g., pain, erythema, swelling, pruritus, warmth, hematoma, induration) must be recorded as AEs on the CRF. In general, these events will be temporally related to the injection.

10.9 Toxicity Management

The Investigator should employ best medical judgment in determining how to manage AEs. Any questions regarding AE management should be directed to the Medical Monitor.

10.10 Risks for Women of Child-Bearing Potential or During Pregnancy

The risks of XT-150 administration during pregnancy have not been evaluated. Male and female participants who are heterosexually active and not surgically sterile must agree to use effective contraception, including abstinence, for the duration of the study.

11.0 ASSESSMENT OF EFFICACY PARAMETERS

Efficacy assessments will be recorded throughout the study (up to Study Day 360) per the Schedules of Assessments and Procedures in Table 1 and Table 2.

The primary efficacy outcome measure is:

 Whether the subject achieves at least a 30% improvement from baseline in WOMAC Pain Score at Day 180, as recorded on a 0 to 20 point scale with 20 being the maximum (worst) score

Secondary efficacy outcome measures:

- Change from baseline in the WOMAC Function Score at Day 180
- Change from baseline in patient response, at Day 180, to the question:
 "Considering all the ways the OA in your knee affects you, how are you doing today?", using a scale of 1 5, with 1 being very good (asymptomatic and no limitation of normal activities) to 5, very poor (very severe, intolerable symptoms and inability to carry out normal activities)

Additional outcome measures include:

- Total and individual parameter scores for the Brief Pain Inventory of Intensity and Interference (BPI)
- The Knee Outcome and Osteoarthritis Scores (KOOS)

12.0 ASSESSMENT OF ANTI-IL-10 ANTIBODIES

Presence of anti-IL-10 antibodies in serum will be assessed. Whole blood for detection of anti-IL-10 antibodies will be drawn at Baseline/Day1, then on Days 7, 30, 60, 180, and 360, then processed to serum. Testing will be conducted following completion of the study.

Procedures for collection, storage, and shipping of immunogenicity samples are described in the study Laboratory Manual.

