6.0 STUDY DESIGN

6.1 Description of the Study

This is a Phase 2 safety, tolerability, and efficacy study of XT-150 in adult participants with pain due to osteoarthritis of the knee. The study will be conducted in 2 Stages, A and B.

Stage A is placebo controlled for six months following intra-articular injection in the Index Knee, which is defined by Kellgren-Lawrence grading and participant-reported pain. The primary efficacy endpoint is 30% response rate in WOMAC pain at Day 180.

Stage B continues for an additional six months of safety and efficacy monitoring during which participants can elect for a second injection to the Index Knee. Active 150 μ g or 450 μ g XT-150 will be randomly chosen for the second injection.

Participants will provide informed consent and meet all study eligibility criteria before any study procedures are initiated. FAST (Appendix 4: Focused Analgesia Selection Test) will be used to select patients who reliably report the magnitude of thermal stimulations.

Baseline confirmation of study eligibility will be completed within one day preceding study drug administration. Study drug will be administered by intra-articular (IA) injection into the joint space of the knee.

About 270 participants will be randomly enrolled into 1 of 3 treatment groups (approximately 90 participants/group). Treatment Groups:

- 1. Placebo (1 mL)
- 2. 150 μg XT-150 (1 mL)
- 3. 450 μg XT-150 (1 mL)

The study will be conducted in 2 stages, A and B:

- A. Placebo controlled for 6 months
- B. Continued follow up for 6 months with the option of randomly receiving a single 150 μg or 450 μg injection as the second injection to the Index Knee (knee dosed in Stage A).

Safety parameters and efficacy endpoints for each participant will be evaluated monthly for about 1 year from the first XT-150 dose (Stage A, Day 0)

The Schedules of Assessments and Procedures are presented in Table 1 and Table 2. Day 0 is defined as the day of study drug administration. Subsequent study days are defined by the number of consecutive calendar days after drug administration.

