6.2 Follow up Assessments

All participants will be assessed for physical examination findings and vital signs following signing of the informed consent form (ICF) and for AEs and SAEs, throughout the study for each treatment group.

Serum samples will be collected from all participants to test for the presence of anti-IL-10 antibodies. Samples will be analyzed using a validated assay by an independent, central bioanalytical laboratory. Procedures for collection, storage, and shipping of immunogenicity samples are described in the study Lab Manual.

Efficacy assessments will be performed at the screening visit (WOMAC Pain Score for eligibility), then all measures at Baseline, on Day 7, Day 30, and approximately monthly thereafter for up to 1 year. Efficacy endpoints will be evaluated at each study visit and overall.

A telephone call documenting safety and efficacy assessments may be used for participants unable to physically attend follow up visits due to COVID-19 infection or corona virus exposure concerns. Home services may be employed for blood collections.

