9.2 Baseline

Baseline assessments may be completed the day before or day of study drug administration, before the XT-150 injection.

- Training for accurate pain reporting
- Brief physical exam, including examination of Index Knee
- Obtain any changes from the complete medical history.
- Record any changes or updates in medications, including pain medications and therapies administered since Screening visit.
- Efficacy assessments

- o Record Baseline BPI scores (Appendix 2)
- o Record Baseline KOOS (Appendix 3)
- OA in your knee affects you, how are you doing today?" on a scale of 1 to 5, 1 being very good (asymptomatic and no limitation of normal activities) to 5, very poor (very severe, intolerable symptoms and inability to carry out normal activities)
- o Record baseline non-prescription pain therapies or practices
- 0
- Clinical assessments
 - Measure vital signs (temperature and the site collected [oral, rectal, temporal, or tympanic], heart rate, blood pressure, and respiratory rate)
- Laboratory assessments
 - Obtain serum for analysis of anti-IL-10 antibodies
- Confirm participant qualification by inclusion/exclusion criteria. Enroll participant prior to dosing

9.3 Day 0

- Before administering study drug:
 - Confirm that all study criteria are met (inclusion and exclusion)
 - Brief physical exam
 - Injection site examination of the Index Knee
 - Record any ongoing medical observations that occurred since Screening visit
 - Record any new AEs since Screening
 - Record any concomitant medications since Screening including prescription, OTC, and herbal medications. Ensure no excluded medications.
- Administer study drug (Section 8.0 for details on preparation)
 - Aseptic techniques will be used in the preparation and administration of XT-150.
 - Injections to the knee space will be guided by ultrasound, fluoroscopy or equivalent visualization
 - All injections of study drug must be performed by a specialist who is qualified, trained, and experienced to perform intra-articular injections
 - Examine injection site for infections or reactions
- Clinical assessments

- Monitor Participant for signs of study drug reaction
- Measure vital signs (temperature, heart rate, blood pressure, and respiratory rate) at least once about 1 hour after injection
- Refresh training on accurate pain reporting

9.4 Between clinic visits:

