13.6 Bioanalytical Analyses

Whole blood samples from participants who received the XT-150 will be analyzed for anti-IL10 antibodies using a validated assay. Any detection of anti-IL-10 antibodies will be described by treatment and timepoint.

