#### 5.5. Data Derived by Calculation

The following data fields for inclusion in the data listings will be derived by calculation as per the Clinical Data Interchange Standards Consortium (CDISC) standard:

Adverse Events:

• Treatment for adverse event, assigned as

```
Non-Treatment-Emergent if (Onset Date) < (Date of Stage A Dose)
```

[figure not shown]
Treatment for Stage A if
(Onset Date) >= (Date of Stage A Dose) &
(Onset Date) < (Date of Stage B Dose);

Treatment for Stage B if (Onset Date) >= (Date of Stage B Dose)

CONFIDENTIAL Page 12 of 27

Protocol No.: XT-150-2-0204 Sponsor: Xalud Therapeutics, Inc.

- Adverse event time since Stage B dose (in days), calculated as
   (Onset Date) (Date of Stage B Dose) if (Onset Date) >= (Date of Stage B
   Dose)
- Adverse event time since Stage B dose is Not Applicable if if (Onset Date) < (Date of Stage B Dose)

- Adverse event duration (in days), calculated as (Resolution Date

  – Onset Date)

Safety Assessments Change from Baseline:

Baseline for vital signs and clinical laboratory parameters will be the most recent
assessment prior to first dose [which may be an unscheduled assessment, a repeat of
a scheduled Baseline assessment, or the screening assessment if separate Baseline
assessments are not performed]

Clinical Safety Laboratory Assessments:

- If a clinical laboratory result is above the upper limit of normal, then Out of Range flag will be set to "H"
- If a clinical laboratory result is below the lower limit of normal, then Out of Range flag will be set to "L"
- Clinical Laboratory parameters that are outside the reference range and medically assessed as clinically significant will be identified as "Abnormal CS"
- Clinical Laboratory parameters that are outside the reference range and not medically assessed as clinically significant will be identified as "Abnormal NCS"

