Any detection of anti-IL-10 antibodies will be summarized by treatment and timepoint.

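### Anti-IL-10 antibodies are summarised only as any detection by visit, so new positivity after dosing is not separated from positivity at baseline and no converter count is specified

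*Protocol*

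**What the plan says.** Protocol 12.0 gives the sampling times: "Whole blood for detection of anti-IL-10 antibodies will be drawn at Baseline/Day1, then on Days 7, 30, 60, 180, and 360". Protocol 9.2 lists this serum among the baseline procedures and fixes their timing: "Baseline assessments may be completed the day before or day of study drug administration, before the XT-150 injection". A pre-dose result should therefore exist for each dosed participant.

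The analysis is stated once in each document. Protocol 13.6: "Any detection of anti-IL-10 antibodies will be described by treatment and timepoint". SAP 8.2: "Any detection of anti-IL-10 antibodies will be summarized by treatment and timepoint".

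The SAP's baseline rule for safety changes (section 5.5) opens with "Baseline for vital signs and clinical laboratory parameters will be the most recent" and does not mention antibodies. SAP 8.1 lists the clinical laboratory tests as hematology, serum chemistry and coagulation, so the antibody assay does not come in under that heading either.

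The visible text gives no definition of treatment-emergent antibody positivity, no shift from baseline, no rule for participants positive before dosing, and no count of those ever positive after dosing.

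**The concern.** Safety and tolerability are the primary objective (Protocol 5.0), and the antibody assay is a named safety assessment (Protocol synopsis, SAP 4.6). The natural question is whether XT-150 induces antibodies. Table 3 of Protocol 4.3 reports the first trial in those terms, stating that no anti-drug antibodies were induced.

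Prevalence at a visit is a different quantity. It adds together participants who were positive before the injection and stayed positive, and participants who became positive afterwards. It also shows each visit separately, so the same positives seen four times cannot be told apart from different participants turning positive at each visit.

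The SAP already makes this separation elsewhere. Section 5.5 classes adverse events with onset before the Stage A dose as not treatment-emergent, and section 8.2 summarises laboratory results and vital signs as change from baseline. Antibodies also have a pre-dose sample but get no equivalent.

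**Working it through.** The documents give no antibody rate, so there is no planned figure to reproduce. The check asks what a by-treatment, by-timepoint table can and cannot tell the reader.

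**Inputs.** n = 90 per Stage A arm (Protocol 13.1). Four post-dose samples in Stage A: Days 7, 30, 60 and 180 (Protocol 12.0). All positivity counts and rates below are assumptions.

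**Step 1: converters at one visit.** Let b be the number positive at baseline and t the number positive at a later visit, with both samples available for everyone. If k participants are positive at both, the converters are c = t − k. The table shows b and t but not k, so c is known only within

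max(0, t − b) ≤ c ≤ min(t, n − b).

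| Baseline positive | Later positive | Any-detection rate | Converters that fit | Over baseline-negatives |
|---|---|---|---|---|
| 0 of 90 | 5 of 90 | 5.6% | 5 | 5/90 = 5.6% |
| 5 of 90 | 5 of 90 | 5.6% | 0 to 5 | 0/85 to 5/85 = 0% to 5.9% |
| 5 of 90 | 8 of 90 | 8.9% | 3 to 8 | 3/85 to 8/85 = 3.5% to 9.4% |
| 9 of 90 | 9 of 90 | 10.0% | 0 to 9 | 0/81 to 9/81 = 0% to 11.1% |

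Apart from the extreme where everyone is positive, the range closes to one value only when no one is positive at baseline, or trivially when no one is positive at that visit.

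**Step 2: cumulative converters.** Suppose no one is positive at baseline and 3% are positive at each of the four Stage A visits. If they are the same people, 0.03 × 90 = 2.7, about 3 of 90, have converted. If they are different people each time, 4 × 2.7 = 10.8, about 11 of 90 (12%), have converted. The per-visit table is identical in both cases. It gives the cumulative number only if positives appear at no more than one post-dose visit.

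**Step 3: persistence of baseline positives.** With pre-existing positivity of 1% to 10% that persists, 0.01 × 90 = 0.9 to 0.10 × 90 = 9 participants per arm, or 1.8 to 18 across the 180 in the two XT-150 arms, would be positive after dosing with no conversion at all. They would also be visible in the baseline row.

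**The case against.** The strongest case on the other side has four parts.

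**Baseline is itself a timepoint.** A reader might infer that the baseline result goes unused, or that pre-existing positives will be counted as drug findings. The documents do not support either reading. A table by timepoint can carry a baseline row, and neither Protocol 13.6 nor SAP 8.2 attributes a detection to XT-150. What remains is that post-dose counts are not split by baseline status.

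**Conversion may still be recoverable.** A reader might infer that conversion will never be reported. That cannot be established. SAP 8.2 lists all safety data by subject, so conversion could be read by hand, and the lists of planned listings and tables (SAP Appendices 1 and 2) are blank in the public copy. The supportable statement is that the visible text specifies no conversion summary. A listing is not a prespecified count with a denominator.

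**The placebo arm is a control.** If placebo samples are assayed, randomisation balances pre-existing positivity in expectation, and an excess in the XT-150 arms would show. This stands in part. It depends on placebo being tested, on which the protocol is not consistent: section 6.2 says "Serum samples will be collected from all participants to test for the presence of anti-IL-10 antibodies", while section 13.6 says "Whole blood samples from participants who received the XT-150 will be analyzed for anti-IL10 antibodies using a validated assay". Even with placebo tested, a difference in prevalence at a visit is not a count of converters.

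**The magnitudes are assumed, and the summary is descriptive.** Both are true. Table 3 of Protocol 4.3 is reassuring for the first trial, and if no one is positive at baseline the planned table gives converters at each visit exactly. The 12% above is an arithmetic bound, not an expected result. The summary drives no test, endpoint or stopping rule.

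**Conclusion.** The point holds as a cheap improvement, not as a flaw in a primary result. As stated in the visible text, the antibody summary cannot separate new from persistent positivity at a visit unless baseline positives are zero (or the visit has none), and it does not in general give the number who convert at any time after dosing. The data needed are already collected.

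The size is unknown because the documents give no rates. On assumed counts of 5 of 90 at baseline and 5 of 90 later, the planned table fits a conversion rate anywhere from 0% to 5.9% of baseline-negatives. The bounds assume everyone has both samples; missing samples would widen them.

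The label in Protocol 12.0 that pairs baseline with Day 1 is a clerical matter only. Since "Day 0 is defined as the day of study drug administration", Day 1 falls after the injection, and a reader might infer that the baseline sample is post-dose. Protocol 9.2 and Table 1 place the draw before the injection, so the analysis is not affected.

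**What to change.** In SAP 8.2 and Protocol 13.6, add treatment-emergent antibody positivity as the main immunogenicity summary:

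- **Definition:** negative before dosing and positive at any of Days 7, 30, 60 or 180. Protocol 9.6 places any Day 180 second injection after that visit's efficacy and safety assessments, so this window reflects the first injection.
- **Denominator:** baseline-negative participants with at least one post-dose result.
- **Grouping:** Stage A treatment actually received, in line with the Safety Population (Protocol 13.2, SAP 6).
- **Baseline positives:** a separate row.
- **Day 360:** conversion reported separately, by treatment sequence received, because some participants will have had a second injection by then.
- **Support:** keep the by-timepoint table.

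The SAP Addendum states that its own analyses were defined after database lock and unblinding. If this table is added at that stage, label it post hoc.

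Correct the baseline label in Protocol 12.0 to match the pre-injection draw, and reconcile Protocol 6.2 with 13.6 on whose samples are tested.

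The cost is some wording and one additional table. No new samples or assays are needed.

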13.0 STATISTICAL METHODS

Efficacy will be assessed at baseline (before XT-150 injection) and at each study visit, starting at Day 7 [± 1 day].

All participants will be included in the safety analysis.

A comprehensive Statistical Analysis Plan (SAP) will be prepared and finalized before database lock. Descriptive statistics (mean, standard deviation, median, minimum, and maximum for continuous variables and count and percentages for categorical variables) for demographics and other baseline characteristics will be provided by treatment group for all participants in the Intent-to-Treat (ITT) and Safety Populations.

13.1 Determination of Sample Size

A total of 270 subjects will be randomized to the 3 treatment groups in a 1:1:1 ratio. The sample size of 90 subjects per group provides more than 90% power to detect a greater responder rate in at least one XT-150 group compared to placebo and 85% power to detect both arms superior to placebo, assuming the responder rate is 30% in each XT-150 group and 10% in the placebo group. As a sensitivity analysis of different assumptions on the response rates in the placebo and XT-150 groups, Table 7 shows the statistical power to detect that at least one treatment group provides greater response than placebo and to detect that both treatment groups provide greater responses.

		Statistical Power (%)				
Placebo response rate (%)	XT-150 response rate (%) in both treatment arms	To detect at least one treatment arm superior to placebo	To detect both treatment arms superior to placebo			
10	25	78	57			
	30	95	85			
	35	99	97			
15	25	38	18			
	30	70	46			
	35	91	77			

Table 7. Treatment Effect That Can Be Detected

13.2 Analysis Populations

The Intent-to-Treat (ITT) Population will comprise all enrolled participants who received the treatment injection, analyzed according to randomized treatment. The ITT Population will be the primary analysis population for efficacy.

The Safety Population will comprise all participants who receive any amount of study drug, analyzed according to treatment actually received.

13.3 Analysis of Study Population and Participant Characteristics

Demographics (including age, race, and gender), medical history including history of pain medication use, Baseline assessments (including height, weight, BMI, WOMAC Pain Score, BPI, and KOOS), clinical signs and symptoms, and administration of study drug will be summarized in the ITT and Safety Populations.

13.4 Safety Analyses

All participants who receive any amount of study drug (Safety Population) will be included in the safety analyses.

Safety will be evaluated by presenting summaries of AEs and vital signs. Safety variables will be tabulated by treatment group.

Adverse events will be graded using the CTCAE v5.0 and will be coded using the Medical Dictionary of Regulatory Affairs (MedDRA®), Version 18 or higher. AEs will be collected for each participant from the signing of the informed consent through the last study visit on Day 360.

A treatment-emergent adverse event (TEAE) is defined as an AE that occurs during or after study drug administration. The incidence of TEAEs will be presented by system organ class (SOC) and preferred term (PT), by SOC, PT, and relationship to the study drug administration, and by SOC, PT, and severity. In addition, the incidence of serious TEAEs and TEAEs leading to discontinuation of study drug will be presented by SOC and PT.

Descriptive statistics for clinical laboratory test results, and vital signs, and for changes from Baseline, will be presented by time point. Baseline is defined as the measurement closest to, but prior to, the administration of study drug. Incidences of potentially clinically significant clinical laboratory results, and vital signs, as defined in the SAP, will also be summarized by time point. A summary of abnormal physical examination findings will also be presented.

13.5 Analysis of Efficacy

All inferential analyses of efficacy will be based on the first 180 days after dose administration (Stage A) and on the analysis of time from Day 0 until patient request for a second injection (see Section 13.5.4). Other analyses of data from Stage B and comparisons between Stage A and B will be descriptive; such analyses will be specified in the SAP.

13.5.1 Multiplicity of endpoints

The statistical analysis of the primary endpoint will preserve a familywise error rate of 0.025 (one-sided), accounting for statistical tests of each of the two XT-150 doses to placebo with respect to the primary endpoint.

[figure not shown]
P-values from analyses of other endpoints may be interpreted as descriptive statistics.

13.5.2 Statistical methods for the binary outcomes

Whether the subject achieves at least a 30% improvement from baseline in WOMAC Pain Score at Day 180 will be coded as a binary outcome: responder or non-responder. Subjects who withdraw from study before Day 180 or otherwise do not provide a response at that time point will be considered non-responders. The response outcome will be analyzed in a logistic regression model with treatment as the main factor and baseline WOMAC pain as a covariate. Within this model, z-tests will be used to compare the two XT-150 doses to placebo, with step-down Dunnett-like adjustments for multiplicity of doses. Handling of special cases, such as zero responders in a treatment group, will be addressed in the SAP.

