#### 9.3. Efficacy Analysis

All inferential analyses of efficacy will be based on the first 180 days after dose administration (Stage A) and on the analysis of time from Day 0 until patient request for a second injection.

CONFIDENTIAL Page 18 of 27

Final 2.0, 11 Oct 2021

Sponsor: Xalud Therapeutics, Inc.

Protocol No.: XT-150-2-0204

[figure not shown]
For the statistical analysis of the primary efficacy endpoint, a logistic regression (response: 30% improvement at Day 180 (yes/no)) will be performed to compare 150 µg XT-150 with placebo and 450 µg XT-150 with placebo statistically. The model will include a fixed effect for treatment and the subject's baseline WOMAC pain score as a covariate. From this model, the 150 µg XT-150 to placebo and 450 µg XT-150 to placebo odds ratio of reduction and its two-sided 95% CI will be calculated. In this analysis, a subject who does not provide a response at Day 180 will be considered a non-responder (i.e., improvement will be set to "no").

In the event that one or more treatment arms has no responders, which would cause numerical difficulties in the logistic regression model, the statistical analysis will add 2 successes and 2 failures to each treatment group. This based on the recommendation in Agresti and Caffo, "Simple and Effective Confidence Intervals for Proportions and Differences of Proportions Result from Adding Two Successes and Two Failures," The American Statistician, Vol. 54, No. 4 (Nov., 2000), pp. 280-288.

The change from baseline in WOMAC Function Score will be analyzed using a repeated measures model including fixed effects for treatment (i.e., 150 µg XT-150, 450 µg XT-150, placebo), study day (i.e., Day 7, 30, 60, 90, 120, 150, 180) and treatment by study day interaction. In addition, the subject's baseline score will be included as a covariate. From the model, the treatment differences between 150 µg XT-150 and placebo, and 450 μg XT-150 and placebo will be estimated for the average effect of the first 180 days after dose administration (i.e., Stage A). Additionally, p-values and corresponding two-sided 95% confidence intervals will be provided.

The change from baseline in WOMAC Pain Score will be analyzed similarly.

Change from baseline in total and individual BPI, change from baseline in KOOS, and change from baseline in the patient response will be analyzed similarly.

CONFIDENTIAL Page 19 of 27

Final 2.0, 11 Oct 2021

Protocol No.: XT-150-2-0204 Sponsor: Xalud Therapeutics, Inc.

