#### **WOMAC Pain Score Change from Baseline**

WOMAC Pain Score Change from Baseline will be summarized with summary statistics by visit and treatment group. Analyses will be performed for both the ITT population and mITT population.

A Mixed Model analysis will be conducted and mixed model statistics (LSMean, StErr, LSMeans Diff and 95% CI of LSMeans diff) – generated for Day 180 and Day 360 (covariates include site, baseline WOMAC Pain, K/L and sex). The effect size at Day 180 and Day 360 using Cohen's d will be calculated from the observed mean and standard deviations and presented.

A summary line plot of WOMAC Pain Mean Change from Baseline by visit and treatment group (with Standard Error at each visit) will be generated.

The following additional exploratory analyses will be performed for the WOMAC Pain Change from Baseline using the same MMRM model to compare treatment groups:

• Stage B (Day 360) analyses comparing treatment groups placebo/150 and placebo/450 to assess the difference between these groups and the assumption of combining them for the placebo/active treatment group.

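### The Stage A efficacy models adjust only for the last pre-dose score; pre-specifying the screening WOMAC Pain score and K-L grade would probably have given a small gain in power at very little cost

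*Protocol*

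**What the plan says.** **Primary endpoint.** Protocol 13.5.2: "The response outcome will be analyzed in a logistic regression model with treatment as the main factor and baseline WOMAC pain as a covariate". SAP 9.3 agrees: "The model will include a fixed effect for treatment", plus the baseline WOMAC pain score and nothing else.

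**Continuous and graded endpoints.** Protocol 13.5.3 and SAP 9.3 use a repeated-measures model with treatment, study day, their interaction and the endpoint's own baseline. Protocol 13.5.3 leaves room for other models but names no covariates for them.

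**Baseline.** SAP 5.5 takes the last assessment before the first dose. When a Day 0 score exists, the screening score enters no model.

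**What else is known before dosing.** Protocol 6.2: "Efficacy assessments will be performed at the screening visit (WOMAC Pain Score for eligibility". Table 1 marks KOOS/WOMAC at both Screening and Day 0. Protocol 9.1 records K-L grade at screening, and the synopsis plans five centres in two countries. BPI and the OA question start at Day 0 in Table 1, with no screening value.

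**Addendum.** The mixed model for WOMAC Pain change uses other terms: "covariates include site, baseline WOMAC Pain, K/L and sex". The Addendum's introduction says its analyses were set after database lock and unblinding, and calls them post hoc.

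**The concern.** Response means a fall of at least 30% from the Day 0 score, so error in that one reading enters the threshold itself. Take a participant whose usual score is 10. If Day 0 reads 10, response needs a Day 180 score of 7 or less (0.7 × 10 = 7). If Day 0 happens to read 12, a score of 8 is enough (0.7 × 12 = 8.4).

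A model with the Day 0 score alone cannot tell a chance-high reading from truly worse pain. A second pre-dose reading can do so in part. K-L grade may add further prognostic information. Both are needed for eligibility, so they should be complete for everyone dosed.

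What is at stake is efficiency. Pre-specified adjustment can raise the power of the primary test and tighten the estimates for continuous endpoints without more participants. The same adjustment chosen after unblinding has no confirmatory standing.

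**Working it through.** **1. Inputs from the documents.** "A total of 270 subjects will be randomized to the 3 treatment groups in a 1:1:1 ratio", so 90 per arm. Power was calculated "assuming the responder rate is 30% in each XT-150 group and 10% in the placebo group". Protocol 13.5.1 sets the familywise error rate at 0.025, one-sided. The stated result is "85% power to detect both arms superior to placebo", and Table 7 gives 95% for at least one arm.

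**2. Reproducing the stated power with no covariates.** Three binomial arms of 90 were simulated with step-down Dunnett testing (first critical value 2.212, correlation 0.5):

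| Test | At least one arm | Both arms |
|---|---|---|
| Stated (Table 7) | 95% | 85% |
| Fisher exact | 94.9% | 83.5% |
| Continuity-corrected z | 94.7% | 83.3% |
| Logit Wald z | 96.1% | 87.6% |

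The planned power therefore does not rely on covariate adjustment. SAP 10 drops the step-down; single-step Dunnett gives 80.5% to 82.8% for both arms by z-test. That is a separate matter, but it is the level from which any gain starts.

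**3. Continuous WOMAC Pain, by formula.** Let *r* be the correlation of each pre-dose score with the Day 180 score, and *b* the correlation between screening and Day 0. Both are assumed. Residual variance, as a share of the total, is 1 − r² with one pre-dose score and 1 − 2r²/(1 + b) with two.

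- r = 0.3, b = 0.8: 0.910 falls to 0.900, a cut of 1.1%.
- r = 0.5, b = 0.7: 0.750 falls to 0.706, a cut of 5.9%.
- r = 0.6, b = 0.6: 0.640 falls to 0.550, a cut of 14.1%.

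The upper figure keeps *b* at or above *r*. With r = 0.6 and b = 0.5 the formula gives 1 − 0.520/0.640 = 18.8%, but a six-month correlation above the one-month correlation is implausible. The formula treats both readings as equally informative and covers one visit; SAP 9.3 estimates an average over the Stage A visits.

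**4. Screening score alone, by simulation.** Assumptions: integer 0–20 scores, entry at 8 or more on both occasions, true SD 2.5, measurement SD 1.3–1.8, change SD 1.5–2.5, and responder rates 10%/30% and 30%/50%. Two sets of six scenarios were run (3,000 trials per scenario at cut-off 2.18; 2,000 at 2.212).

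- The screening–baseline correlation was 0.55–0.70 in the first set and 0.53–0.69 in the second.
- Information in the primary z-test (ratio of squared mean z) rose by a factor of 1.027–1.056 and 1.026–1.052. On 270 participants, 1.027–1.056 is worth about 7 to 15 more (270 × 0.027 = 7.3; 270 × 0.056 = 15.1).
- Both-dose power rose by 0.5–4 and 1.5–2.8 points. Examples are 82.1% to 84.2%; 80.4% to 82.8% at 10%/30%; and 54.9% to 57.7% at 30%/50%.
- Residual variance fell by about 6–9% in both sets, which makes intervals about 3–5% narrower (√0.94 = 0.970; √0.91 = 0.954).

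**5. Screening score, K-L grade and four site indicators together.** Six scenarios of 3,000 trials, cut-off 2.212. Power for at least one dose rose by 0 to 1.0 point, from a start of about 96–97%. Both-dose power changed by −0.2 to +5.5 points: 81.1% to 82.6% with r = 0.5, b = 0.7 and no K-L or site effect, and 79.9% to 85.4% with r = 0.6, b = 0.7 and strong assumed K-L and site effects. Monte Carlo error is about 0.7 point per both-dose estimate. The standard error of the log odds ratio rose, from about 0.42–0.44 to 0.44–0.46, while the odds ratio moved away from 1.

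**6. Room for extra terms.** Expected responders are 9 + 27 + 27 = 63. The planned model has 3 non-intercept terms. Screening score and K-L grade make 5 (63/5 = 12.6 responders per term). Four site indicators make 9 (63/9 = 7), with 9/5 = 1.8 placebo responders per site.

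**The case against.** The strongest reply is that nothing is wrong. The planned model is unbiased under randomisation, already holds a natural prognostic covariate and reaches its stated power. All of that stands, and it is why this is an efficiency point only.

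The size is assumed. The documents give no correlations and no K-L effect, and the gain could be close to nil. The screening score is one more noisy reading, up to 30 days older and restricted by the entry cut-off, so it removes only part of the Day 0 noise. This stands too.

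Three stronger readings are tempting and not supported:

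- *Precision is lost in the primary analysis.* A reader might expect narrower intervals for the odds ratio. Step 5 shows the reverse on the log scale. The wording fits only the continuous endpoints.
- *Site belongs in the primary model as well.* With fewer than 2 expected placebo responders per site, it would need a pooling rule. It would also complicate the SAP 9.3 rule that adds two successes and two failures per group, since the added records would need site values.
- *A second pre-dose score exists for every endpoint.* It is certain only for WOMAC Pain. WOMAC Function and KOOS rest on the combined row in Table 1, and BPI and the OA question have none.

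Nor does the Addendum show that the sponsor found the primary model deficient. It centres on Stage B, models continuous change and does not use the screening score.

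Finally, the database has since been unblinded, so a change to SAP 9.3 can no longer count as pre-specified for these data. That limits what can be recovered now. It does not make the plan as written the better choice.

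**Conclusion.** The point holds as a modest missed efficiency. The Stage A models leave out two baseline variables collected on everyone: the screening WOMAC Pain score and K-L grade.

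Under the assumed correlations, the screening score adds about 0.5 to 4 points of both-dose power. It lowers residual variance for WOMAC Pain change by about 1% to 14%, and by 6% to 9% in the central scenarios. At-least-one-dose power changes by 0 to 1 point, even with K-L grade and site included. K-L grade would add whatever prognostic value it has, which the documents do not let one estimate.

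The validity of the planned test and the 95%/85% power claim are not in question. The Addendum's adjusted model, defined after unblinding, cannot do the work of a pre-specified one.

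**What to change.** The change belonged in SAP 9.3 before unblinding:

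- **Primary logistic model:** add the screening WOMAC Pain score and K-L grade (2 v 3). Leave site out.
- **Repeated-measures models:** add K-L grade, site, and the screening value of the endpoint where one was recorded. That is certain for WOMAC Pain, to be confirmed for WOMAC Function and KOOS, and not available for BPI or the OA question.
- **Baseline-only logistic model:** keep it as the sensitivity analysis, and as the model used if the zero-responder rule applies.

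The cost is some SAP text and two extra parameters in the primary model, with no new data. The reported odds ratio becomes conditional on two more variables and will tend to lie slightly further from 1, so it should be described that way. If run on the unblinded data, the adjusted model should be labelled post hoc. The same terms can be pre-specified in the next trial.
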